1) STUDY SYNOPSIS

Name of Sponsor	Opiant Pharmaceuticals
Name of Investigational Product:	Nalmefene hydrochloride nasal spray
Title of Study:	An Open-Label, Three-Period, Three-Treatment, Six-Sequence, Randomized Crossover Study of the Pharmacokinetics of Intranasal Nalmefene in Healthy Volunteers using Three Dosing Regimens
Clinical Phase:	Phase I (Healthy Volunteers)
Protocol Number:	OPNT003-PK-002
Study Design:	
Open-label, randomized, 3-period, 3-treatment, 6-sequence, randomized crossover study in 24 healthy volunteers. Subjects will be assigned to each of the 6 possible sequences.
 
Each subject will receive 3 intranasal (IN) Nalmefene doses:
 
• 3mg IN dose (one 0.1mL spray of a 30mg/mL solution in one nostril)• 6mg IN dose (one 0.1mL spray of a 30mg/mL solution in each nostril)• 6mg IN dose (two 0.1mL sprays of a 30mg/mL solution in one nostril) 
There will be a 6 day washout period between doses. Screening can occur up to 28 days before admission, subjects will then stay in the inpatient facility for 16 days to complete the treatment phase of the study and will be discharged following completion of the discharge procedures at the end of the last period. Subjects will be called 3 to 5 days after discharge to inquire concerning Adverse Events (AEs) and concomitant medications since discharge.
 
All subjects who have given their written informed consent and who satisfy all of the relevant inclusion criteria and none of the exclusion criteria will be screened for eligibility to participate in the study including medical history, demographics, concomitant medications, physical examination, height, weight, body mass index (BMI), nasal passage examination, smell test, clinical chemistry, coagulation markers, hematology, serum Follicle Stimulating Hormone (FSH) levels (females postmenopausal

	
only), infectious disease serology, urinalysis, urine drug, urine cotinine and urine alcohol toxicology screen, serum pregnancy test (females only), vital signs and electrocardiogram (ECG).
 
On the day of clinic admission (Day -1) the following procedures will be performed to review eligibility, update on medical history, update on concomitant medications, physical examination, nasal passage examination, 12-lead ECG, vital signs, urine pregnancy test (females only), urine drug, urine cotinine and urine alcohol toxicology screen.
 
After eligibility of established and admission procedures has been reviewed by an investigator, patients will be randomized.
 
On the day after admission subjects, in a fully supine position, will be administered the IN dose randomized to a sequence order of receipt.
 
Subjects should be instructed to hold their breath during administration of the nasal spray into the nose. Blood will then be collected prior to dosing (within 15 minutes) and approximately 2.5, 5, 7.5, 10, 15, 20, 30, 45 minutes and 1, 2, 3, 4, 6, 8, 12, 18, 24 and 48 hours after drug administration. Pre-dose blood sample will be collected within 15 minutes before dosing.
 
Actual blood collection times can vary as follows: \pm30 seconds for the 2.5, 5 & 7.5 samples, \pm1 minute for the 10 to 30-minute samples, \pm3 minutes for the 45 to 120-minute samples, and \pm5 minutes for the 180 minute or greater samples. Actual sampling times will be recorded.
 
On days of study drug administration (days 1, 7 and 13): A numerical rating scale (NRS) to assess acute nasal pain will be completed pre-dose, and at approximately 15 (\pm 2) and 60 (\pm 10) minutes post-dose. Continuous cardiac monitoring (telemetry) will be performed from approximately one hour (\pm 30 minutes) pre-dose to 6 hours (\pm 30

--	--

	
minutes) post-dose. ECG assessment will be conducted within \pm 5 minutes of the nominal blood collection at 20 minutes, and \pm 15 minutes of the nominal blood collections at 1 and 6 hours post-dose.
 
Vital signs will be measured pre-dose and at approximately 15 and 30 minutes, and \pm 15 minutes of the nominal blood collections at 1, 2, 4 and 8 hours post-dose. Vital signs will also be measured if the subject displays any change in condition including lightheadedness, dizziness, syncope, nausea, vomiting or tachy/bradyarrhythmia as noted on continuous cardiac monitoring.
 
Nasal passage examination will be conducted in both nostrils pre-dose, at approximately 5 minutes and \pm 15 minutes of the nominal blood collections at 1 and 8 hours post-dose.
 
Smell test will be conducted pre-dose and \pm 15 minutes of the nominal blood collections at 1 and 4 hours post-dose.
 
Tolerability assessed via AE query and concomitant medications will be reviewed.
 
On the day after dosing (day 2,8 and 14) tolerability via AE query will be assessed, concomitant medications reviewed, vital signs measured, the smell test will be conducted and examination of the nasal passage performed in both nostrils at approximately 24 hours post-dose.
 
On the second day after dosing (day 3 and day 9) tolerability via AE query will be assessed, concomitant medications reviewed, vital signs measured and examination of the nasal passage performed in both nostrils at approximately 48 hours post-dose.
 
On days 4, 5, 10 and 11 tolerability will be assessed, and concomitant medications reviewed. On the days before the next dosing (days 6 and 12) tolerability will be assessed, concomitant medications reviewed, a urine pregnancy test (females only) and 12-lead ECG performed. On the day of clinic discharge (day 15) from the inpatient stay the following procedures will be performed: assess tolerability via AE query, update on concomitant medications, vital signs at approximately 48 hours post-dose, physical examination, weight, examination of the nasal passage in both nostrils at approximately 48 hours post-dose, smell test,,

--	--

	12-lead ECG, serum pregnancy test (females only), clinical chemistry, coagulation markers, hematology and urinalysis. AEs will be assessed by spontaneous reports by subjects, by examination of the nasal mucosa and by measuring vital signs, ECG and clinical laboratory parameters.
Planned Sample Size:	Twenty-four subjects
Investigational medicinal product, route of administration and dosage:	Nalmefene hydrochloride 3mg nasal spray Nasal (IN) Period 1: 3mg (one 0.1 mL spray of 30 mg/mL nalmefene hydrochloride in one nostril) Period 2: 6mg (one 0.1 mL sprays of 30 mg/mL nalmefene hydrochloride in each nostril) Period 3: 6mg (two 0.1 mL sprays of 30 mg/mL nalmefene hydrochloride in one nostril)
Maximum Duration of Treatment	Screening can occur up to 28 days before admission. The total subject inpatient stay is 16 days, during which the treatment will be administered. Subjects will be called 3 to 5 days after final discharge to inquire concerning adverse events and concomitant medications since discharge. Total subject duration is up to 48 days to complete the entire study.

1) SCHEDULE OF EVENTS

	Screening	Admission	Period 1	Washout			Period 2	Washout			Period 3	Washout	Discharge or Early term	Follow-Up Phone call				
Study Day(s)	-28 to -2	-1	1	2	3	4	5	6	7	8	9	10	11	12	13	14	15	+3 to 5 days after discharge
Informed Consent	X																	
Medical History (includes smoking history)	X	X																
Demographics	X																	
Eligibility (Inclusion/Exclusion)	X	X																
Physical Examination	X	X															X	
Nasal Passage Examination	X	X	X ^a	X ^b	X ^c		X ^a	X ^b	X ^c		X ^a	X ^b	X ^c					
NRS			X ^d				X ^d				X ^d							
Smell test	X		X ^e	X ^f			X ^e	X ^f			X ^e	X ^f	X					
12-lead ECG ^g	X	X					X				X						X	
Continuous cardiac monitoring (telemetry)			X ^g				X ^g				X ^g							
ECG assessment			X ^h				X ^h				X ^h							
Vital Signs	X ^e	X ^e	X ⁱ	X ^g	X ^h		X ⁱ	X ^g	X ^h		X ⁱ	X ^g	X ^e					
Weight	X																X	
Height, BMI	X																	
Clinical Chemistry & Coagulation parameters ^j	X																X	
Hematology ^k	X																X	
Urinalysis ^l	X																X	
Serum FSH levels (females postmenopausal)	X																	
Serum Pregnancy test (females)	X																X	
Urine Pregnancy test (females)		X					X				X							
Urine drug and alcohol toxicology screen ⁱ	X	X																
Urine cotinine screen	X	X																
HIV, Hepatitis B and C	X																	
PK blood sampling			X ^m	X ⁿ	X ^o		X ^m	X ⁿ	X ^o		X ^m	X ⁿ	X ^o					
AEs			X	X	X	X	X	X	X	X	X	X	X	X	X	X	X	
Concomitant medications	X	X	X	X	X	X	X	X	X	X	X	X	X	X	X	X	X	
Randomization			X															
Study drug administration ^p				X				X								X		
Meals ^q		X	X	X	X	X		X	X	X	X		X	X	X	X	X	
COVID-19 PCR Test		X																

^a Nasal passage examination on both nostrils will be performed at pre-dose, and at approximately 5 minutes (\pm 1 minute) and at 1 and 8 hours post-dose (\pm 15 minutes).

^b Nasal passage examination on both nostrils will be performed at approximately 24 hours post dose (\pm 30 minutes).

^c Nasal passage examination on both nostrils will be performed at approximately 48 hours post dose (\pm 30 minutes).

^d ECG assessment will be conducted at 20 (\pm 5 minutes) minutes, and at 1 (\pm 15 minutes) and 6 (\pm 15 minutes) hours post-dose.

^e Sitting (5 minutes) blood pressure, heart rate, respiration rate, and temperature.

^f Blood pressure, heart rate, respiration rate, pre-dose (within 30 minutes; sitting) and at approximately 15 and 30 minutes (supine), and at 1, 2, 4 and 8 (\pm 15 minutes; sitting) hours post-dose, after at least 5 minutes rest.

^g Blood pressure, heart rate, respiration rate, at approximately 24 hours (\pm 30 minutes; sitting) post-dose, after at least 5 minutes rest.

^h Blood pressure, heart rate, respiration rate, at approximately 48 hours (\pm 30 minutes; sitting) post-dose, after at least 5 minutes rest.

ⁱ Chemistry parameters include: total protein, albumin, blood urea nitrogen, creatinine, alkaline phosphatase, ALT, AST, total bilirubin, glucose, sodium, potassium, chloride, CO₂, total cholesterol, and calcium. Coagulation parameters include PT and aPTT.

^j CBC with differentials and platelet count will be performed.

^k Urinalysis includes: pH, specific gravity, blood, ketones, nitrites, glucose, bilirubin, leukocyte esterase, protein.

^l Urine toxicology screen for alcohol, opioids, cocaine, amphetamine/methamphetamine, benzodiazepines, barbiturates, THC, or methadone.

^m Pre-dose (within 15 mins), 2.5, 5, 7.5, 10, 15, 20, 30, 45 minutes and 1, 2, 3, 4, 6, 8, 12, 18 hours post-dose. Pre-dose blood sample will be collected within 15 minutes before dosing. Actual blood collection times can vary as follows: \pm 30 seconds for the 2.5, 5 & 7.5 samples, \pm 1 minute for the 10 to 30-minute samples, \pm 3 minutes for the 45 to 120-minute samples, and \pm 5 minutes for the 180 minute or greater samples.

ⁿ 24 (\pm 5 minutes) hours post dose.

^o 48 hours post dose (\pm 5 minutes). At discharge, collect sample after last blood draw prior to Final Discharge (or early termination) after the third dosing for clinical chemistry, coagulation markers and hematology.

^p Subjects will receive either 3 mg nalmefene hydrochloride IN (one 0.1 mL spray of 30 mg/mL nalmefene hydrochloride in one nostril), 6 mg nalmefene hydrochloride IN (one 0.1 mL spray of 30 mg/mL nalmefene hydrochloride in each nostril) or 6 mg nalmefene hydrochloride IN (two 0.1 mL sprays of 30 mg/mL nalmefene hydrochloride in one nostril). Subjects must be in a fully supine position at dosing and for 1 hour post-dose. Subjects should be instructed to hold their breath during administration of the nasal spray into the nose.

^q Subjects will fast from midnight the day before nalmefene dosing until one hour after dosing. Water will be provided *ad libitum*.

^r NRS will be performed at pre-dose, at approximately 15 (\pm 2) minutes and 1 (\pm 10 minutes) hour post-dose.

^s Subjects will be supine for at least 5 minutes prior to obtaining ECGs.

^t Smell test will be conducted pre-dose and at 1 and 4 hours post dose (\pm 15 minutes).

1 INTRODUCTION

This document details the planned statistical analyses for Opiant Pharmaceuticals, protocol “OPNT003-PK-002” study titled “An Open-Label, Three-Period, Three-Treatment, Six-Sequence, Randomized Crossover Study of the Pharmacokinetics of Intranasal Nalmefene in Healthy Volunteers using Three Dosing Regimens”.

The proposed analyses are based on the contents of the final version of the protocol (dated 06-AUG-2021).

2 STUDY OBJECTIVES

The primary objective is to compare the pharmacokinetics (PK) of 3mg nalmefene hydrochloride IN spray:

- administered as a single dose in one nostril
- administered as a single dose in both the nostril
- administered as two doses in one nostril

The secondary objective is to

- Evaluate the safety and tolerability of IN nalmefene

3 ENDPOINTS

3.1 Pharmacokinetic Endpoints

The following plasma pharmacokinetic parameters for nalmefene will be calculated using non-compartmental analysis:

- Maximum plasma concentration (C_{max})
- Time to maximum plasma concentration (T_{max})
- Area under the curve to the final time with the concentration equal to or greater than the lower limit of quantification [AUC_{0-t}], to infinity [AUC_{inf}], and during the first 30 minutes [$AUC_{0-2.5\text{ mins}}$, $AUC_{0-5\text{ mins}}$, $AUC_{0-7.5\text{ mins}}$, $AUC_{0-10\text{ mins}}$, $AUC_{0-15\text{ mins}}$, $AUC_{0-20\text{ mins}}$ and $AUC_{0-30\text{ mins}}$].
- Terminal elimination rate constant (λ_z)
- Half-life ($t_{1/2}$)
- Clearance (CL/F)
- Volume of distribution (V_z/F) uncorrected for bioavailability (F)
- Dose-normalized C_{max} and AUCs

QMD Ref: Worldwide-TMP-ST-006-4.0 Effective: 12Aug2019	Governing QMD: Worldwide-SOP-ST-001
Confidentiality Statement	
This document is the property of Worldwide Clinical Trials Inc. and may not be duplicated, copied, altered or removed from company without prior approval from Worldwide Quality Assurance or in compliance with Worldwide Standard Operating Procedures.	

Worldwide Clinical Trials Controlled Quality Management Document		
 WORLDWIDE CLINICAL TRIALS	Sponsor:	Opiant Pharmaceuticals

3.2 Safety Endpoints

Safety endpoints will include:

- Adverse events (AEs)
- Vital signs (heart rate, sitting blood pressure, and respiration rate)
- Electrocardiogram (ECG)
- Clinical laboratory changes
- Numerical rating scale (NRS) measuring acute nasal pain and nasal irritation (erythema, edema, and erosion) determined from the nasal passage examination following each nasal administration of study drug

4 SAMPLE SIZE

This study is intended to obtain information regarding the PK of intranasal naloxone under the conditions of this study. Twenty-four (24) subjects are planned for this study. The sample size was estimated using a power of 80% and an alpha error of 5% for pair-wise comparisons. The power was defined as the probability of having a 90% confidence interval to a Test/Reference ratio within the acceptance criteria of 80.00 – 125.00%. A difference of zero on a log-scale was assumed for pharmacokinetic parameters across treatments. Assuming an inter-subject CV of approximately 10% (based on the ANOVA CV% for AUC_{inf} determined in Protocol OPNT003-PK-001), at least 18 subjects should complete the study; to account for the possibility of dropouts and unexpected variability, 24 subjects will be enrolled. The number of subjects is deemed appropriate for this type of study.

5 RANDOMIZATION

Twenty-four (24) healthy subjects will be randomly assigned to 6 sequences (4 subjects per sequence). Each subject will receive one of the 3 treatments in each of the 3 treatment periods.

The 6 sequences will be assigned as follows:

Sequence	Period 1	Period 2	Period 3
1	Treatment A	Treatment B	Treatment C
2	Treatment B	Treatment C	Treatment A
3	Treatment C	Treatment A	Treatment B
4	Treatment A	Treatment C	Treatment B
5	Treatment B	Treatment A	Treatment C
6	Treatment C	Treatment B	Treatment A

QMD Ref: Worldwide-TMP-ST-006-4.0 Effective: 12Aug2019	Governing QMD: Worldwide-SOP-ST-001
Confidentiality Statement	

This document is the property of Worldwide Clinical Trials Inc. and may not be duplicated, copied, altered or removed from company without prior approval from Worldwide Quality Assurance or in compliance with Worldwide Standard Operating Procedures.

Worldwide Clinical Trials Controlled Quality Management Document		
 WORLDWIDE CLINICAL TRIALS	Sponsor:	Opiant Pharmaceuticals
	Protocol Number:	OPNT003-PK-002

Where,

- Treatment A: 3 mg, one 0.1 mL spray in one nostril.
- Treatment B: 6 mg, one 0.1 mL spray in each nostril.
- Treatment C: 6 mg, two 0.1 mL sprays in one nostril.

6 PLANNED ANALYSES

No statistical analysis plan (SAP) prepared in advance of the data can be absolutely definitive and the final Clinical Study Report (CSR) may contain additional tables or statistical tests if warranted by the data obtained. The justification for any such additional analyses will be fully documented in the final CSR.

6.1 Analysis Populations

Subjects excluded from the Populations and the reason for their exclusion will be listed in Appendix 16.2 of the CSR.

6.1.1 Safety Population

The safety population will include all subjects who receive at least one administration of the study drugs.

6.1.2 Pharmacokinetic Evaluation Population

Pharmacokinetic Analysis Population for Test 2 versus Test 1 Comparison (B vs. A)

The pharmacokinetic analysis population for Test 2 versus Test 1 comparison will include all subjects who have evaluable pharmacokinetic data on the Test 2 period and on the Test 1 period and did not deviate from the protocol in a way that might affect the evaluation of the pharmacokinetic endpoints.

Pharmacokinetic Analysis Population for Test 3 versus Test 1 Comparison (C vs. A)

The pharmacokinetic analysis population for Test 3 versus Test 1 comparison will include all subjects who have evaluable pharmacokinetic data on the Test 3 period and on the Test 1 period and did not deviate from the protocol in a way that might affect the evaluation of the pharmacokinetic endpoints.

Pharmacokinetic Analysis Population for Test 2 versus Test 3 Comparison (B vs. C)

QMD Ref: Worldwide-TMP-ST-006-4.0 Effective: 12Aug2019	Governing QMD: Worldwide-SOP-ST-001
Confidentiality Statement	
This document is the property of Worldwide Clinical Trials Inc. and may not be duplicated, copied, altered or removed from company without prior approval from Worldwide Quality Assurance or in compliance with Worldwide Standard Operating Procedures.	

Worldwide Clinical Trials Controlled Quality Management Document		
 WORLDWIDE CLINICAL TRIALS	Sponsor:	Opiant Pharmaceuticals

The pharmacokinetic analysis population for Test 2 versus Test 3 comparison will include all subjects who have evaluable pharmacokinetic data on the Test 2 period and on the Test 3 period and did not deviate from the protocol in a way that might affect the evaluation of the pharmacokinetic endpoints.

6.2 Derived Data

This section describes the derivations required for statistical analysis. Unless otherwise stated, variables derived in the source data will not be re-calculated.

6.2.1 Study Period / Visits

Each visit as per study schedule will be mapped to treatment period and analysis visit for summary tables as given below. Listings will reflect actual period and visit as defined in protocol.

Collected Visit	Analysis Visit	Analysis Period
Screening	Screening	-
Day -1	Day -1	-
Day 1	Day 1	Period 1
Day 2	Day 2	Period 1
Day 3	Day 3	Period 1
Day 4	Day 4	Period 1
Day 5	Day 5	Period 1
Day 6	Day 6	Period 1
Day 7	Day 7	Period 2
Day 8	Day 8	Period 2
Day 9	Day 9	Period 2
Day 10	Day 10	Period 2
Day 11	Day 11	Period 2
Day 12	Day 12	Period 2
Day 13	Day 13	Period 3
Day 14	Day 14	Period 3
Day 15 (Discharge)	EOS / ET	-
Early Termination	EOS / ET	-
Follow-Up Phone Call	FUP	-

Any Discharge assessments taken more than once will be mapped as "DIS – Unscheduled" in listings.

QMD Ref: Worldwide-TMP-ST-006-4.0 Effective: 12Aug2019	Governing QMD: Worldwide-SOP-ST-001
Confidentiality Statement	
This document is the property of Worldwide Clinical Trials Inc. and may not be duplicated, copied, altered or removed from company without prior approval from Worldwide Quality Assurance or in compliance with Worldwide Standard Operating Procedures.	

Worldwide Clinical Trials Controlled Quality Management Document		
 WORLDWIDE CLINICAL TRIALS	Sponsor:	Opiant Pharmaceuticals

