6.2.4 Baseline

Baseline is defined as the last non-missing value (either scheduled, unscheduled or repeat) before the subject receives the first dose of study drug.

For variables that will be summarized by treatment, the Baseline for each period is defined as the last non-missing value (either scheduled, unscheduled or repeat) that is collected before dosing, in the respective period.

Change from Baseline = Result at visit / timepoint – Result at Baseline

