6.11.3 Vital Signs

All Vital signs except temperature will be tabulated for Baseline, 0.25 h, 0.5 h, 1 h, 2 h, 4 h, 8 h, 24 h and 48 h post-dose and the respective changes from Baseline, per treatment. Temperature will be tabulated for Baseline and EOS/ET and the change from Baseline, per treatment. In addition, vital signs values will be tabulated for Baseline, EOS/ET, and change from Baseline to EOS/ET by treatment sequence and overall.

Descriptive statistics for the following vital signs will be presented:

QMD Ref: Worldwide-TMP-ST-006-4.0 Effective: 12Aug2019	Governing QMD: Worldwide-SOP-ST-001
Confidentiality Statement	

This document is the property of Worldwide Clinical Trials Inc. and may not be duplicated, copied, altered or removed from company without prior approval from Worldwide Quality Assurance or in compliance with Worldwide Standard Operating Procedures.

Worldwide Clinical Trials Controlled Quality Management Document		
 WORLDWIDE CLINICAL TRIALS	Sponsor:	Opiant Pharmaceuticals

- Systolic blood pressure (mmHg)
- Diastolic blood pressure (mmHg)
- Pulse rate (beats/min)
- Respiration rate (breath/min)
- Body temperature (°Celsius)

Also, Shift tables in relation to investigator assessment i.e. Normal, Abnormal NCS (Not Clinically Significant), and Abnormal CS (Clinically Significant), from Baseline to each post-baseline visits will be presented. EOS/ET visit will be presented by Treatment sequence and all other post-baseline visits will be presented by treatment.

All vital sign data, including details of any clinically significant values will be listed.

In Mock Shells: Tables 14.3.5.1 and 14.3.5.2, Listing 16.2.8.10

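### SAP 6.2.1 gives Day 15 no treatment period although it is the Period 3 48-hour time point for by-treatment tables, and 6.11.3 tabulates discharge temperature per treatment with no period to attach it to

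*SAP*

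**What the plan says.** SAP 6.2.1 sets the rule for summary tables: "Each visit as per study schedule will be mapped to treatment period and analysis visit for summary tables as given below". In its table, Days 1 to 6 belong to Period 1, Days 7 to 12 to Period 2, and Days 13 and 14 to Period 3. The row that begins "Day 15 (Discharge" carries the analysis visit EOS/ET and a dash for the period. Early Termination is mapped in the same way.

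The protocol synopsis (Study Design) lists among the Day 15 procedures "vital signs at approximately 48 hours post-dose, physical examination, weight, examination of the nasal passage in both nostrils at approximately 48 hours post-dose". Footnote c of the Schedule of Events, which marks the nasal examination on Days 3, 9 and 15, reads "Nasal passage examination on both nostrils will be performed at approximately 48 hours post dose".

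SAP 6.11.3 tabulates vital signs other than temperature at eight post-dose times, the last at 48 hours, per treatment. SAP 6.11.6 does the same for the nasal examination at five post-dose times, again ending at 48 hours, and adds shifts by treatment.

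On temperature, 6.11.3 says: "Temperature will be tabulated for Baseline and EOS/ET and the change from Baseline, per treatment". The same paragraph also plans vital signs at EOS/ET by sequence and overall. SAP 6.2.4 says: "For variables that will be summarized by treatment, the Baseline for each period is defined as the last non-missing value", and requires that value to be collected before dosing in the same period.

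**The concern.** In a crossover, a record's treatment is identified by sequence and period together. A record without a period therefore has no treatment under the map, so 6.2.1 conflicts with the by-treatment 48-hour displays in 6.11.3 and 6.11.6.

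For vital signs, the Day 15 values still appear at EOS/ET by sequence and overall. For the nasal examination, 6.11.6 plans no EOS/ET display, so on the literal map the Period 3 48-hour results appear in no summary table. SAP 3.2 names as a safety endpoint "nasal irritation (erythema, edema, and erosion) determined from the nasal passage examination following each nasal administration of study drug". The 48-hour column would cover only the first two of the three administrations, and its n would differ from every other column of the same table.

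There is a second possible effect. SAP 6.2.8 imputes a Not Done/Missing record where a scheduled assessment is absent from a shift summary, and the post-lock addendum adds that category to both nasal tables. Completed Period 3 examinations could then be shown as not done.

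The temperature sentence is a separate fault. It asks for a by-treatment change from baseline for a variable that has neither an in-period baseline nor a value belonging to one treatment.

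**Working it through.** **Inputs.** Dosing days 1, 7 and 13 (protocol synopsis). Six sequences of 4 subjects, 6 × 4 = 24 (SAP Section 5), which reproduces the planned sample size. Period map from SAP 6.2.1. Full completion is assumed.

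**Step 1: which period the map gives each time point.**

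| Period | Dosing day | 24-h day → mapped period | 48-h day → mapped period |
|---|---|---|---|
| 1 | 1 | Day 2 → Period 1 | Day 3 → Period 1 |
| 2 | 7 | Day 8 → Period 2 | Day 9 → Period 2 |
| 3 | 13 | Day 14 → Period 3 | Day 15 → none |

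**Step 2: subjects affected per treatment.** Sequences in which each treatment falls in each period:

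| Treatment | Period 1 | Period 2 | Period 3 |
|---|---|---|---|
| A | 1, 4 | 3, 5 | 2, 6 |
| B | 2, 5 | 1, 6 | 3, 4 |
| C | 3, 6 | 2, 4 | 1, 5 |

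Each cell holds 2 × 4 = 8 subjects. At 24 hours all 24 subjects per treatment are mapped. At 48 hours 24 − 8 = 16 are mapped. If only 18 completed, balanced over sequences, the figure would be 12 of 18.

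**Step 3: share of all post-dose assessments.**
- Nasal: 5 times × 3 periods × 24 = 360; 24/360 = 6.7%.
- Vital signs: 8 times × 3 periods × 24 = 576; 24/576 = 4.2%.

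**Step 4: precision.** At equal SD, the standard error of a 48-hour vital-sign mean grows by sqrt(24/16) = 1.22, about 22%. This does not suit the nasal irritation grade, which is ordinal.

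**Step 5: temperature.** The only vital-sign set that includes temperature is footnote e, "Sitting (5 minutes) blood pressure, heart rate, respiration rate, and temperature", used at Screening, Day -1 and discharge or early termination. Footnotes f to h, for the dosing days and the 24- and 48-hour visits, list blood pressure, heart rate and respiration rate only. The superscript on dosing-day vital signs is printed as i, the chemistry footnote; I read it as f. All three temperature visits carry a dash in the map, so 0 of 3 belong to a period. No pre-dose temperature is scheduled within a period, so the baseline that 6.2.4 requires does not exist.

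**The case against.** The best counter-argument is that the map assigns visits, not post-dose times. Days 1, 7 and 13 each hold several time points, and 48 hours spans three analysis visits, so the by-treatment columns must be built on nominal post-dose time anyway. On that reading, the specific 48-hour instructions in 6.11.3 and 6.11.6 prevail, and EOS/ET serves only the by-sequence displays. The Period 3 48-hour PK sample is also a Day 15 record, and nobody would drop it. If Not Done/Missing records were imputed, quality control would probably notice the block. Temperature is not among the vital signs listed in 3.2, and it could be assigned to the last treatment, much as 6.11.1 does for adverse events.

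Part of this stands. A programmer keying on nominal time would keep the records, and the mock shells are not in the documents, so what was programmed is unknown. But the SAP does not write that rule for safety data. For PK it does: 6.2.10.1 lists 48 hours for each period, and 6.3 summarizes concentrations by nominal sample time. The vital-sign shift rule in 6.11.3 points the other way, sending EOS/ET to the by-sequence display and all other visits to the by-treatment one. The addendum moved ECG to by-treatment display because the data arise within treatment periods, yet left 6.2.1, 6.11.3 and 6.11.6 unchanged. The last-treatment rule covers adverse events only, and would not supply the missing in-period temperature baseline.

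**Conclusion.** Both parts hold. Followed as written, 6.2.1 removes one third of subjects (8 of 24 per treatment) from the 48-hour by-treatment vital-sign and nasal columns, and leaves the 24 Period 3 48-hour nasal examinations in no summary table. This rests on full completion and on the literal map being applied. The conflict in the text is certain; the loss in the actual tables is not.

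The consequence is limited. It touches one time point in one period, is balanced over treatments, and affects descriptive tables only. Listings keep the records. Other time points, adverse-event attribution and the PK analysis are unaffected. It should still be corrected, because a named safety endpoint is involved and the written rule gives the wrong table.

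The per-treatment temperature table has no valid interpretation under the plan's own baseline definition. In completers its single post-dose value follows all three treatments.

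**What to change.** 1. In SAP 6.2.1, add a line mapping the Day 15 48-hour vital signs and nasal examination to Period 3, 48 h, for the by-treatment tables and shifts. Keep the EOS/ET mapping for the by-sequence tables. Limit the new line to Day 15 discharge records, because an early-termination visit need not fall 48 hours after a dose.
2. In SAP 6.11.3, delete the sentence tabulating temperature per treatment. The EOS/ET display by sequence and overall in the same paragraph already presents these data.

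The cost is one line, one deletion, and a check, with minor reprogramming if needed, of Tables 14.3.5.1, 14.3.5.2, 14.3.6.4.1 and 14.3.6.4.2. The latest SAP document is a post-database-lock addendum, so the change would need a further addendum or, as SAP Section 7 provides for deviations, a written justification in the CSR. No valid information is lost.
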